10.1 Verification of Scan Results

10.1.1 Biopsy of Suspected Metastases

Biopsy of metastatic sites of prostate cancer patients is feasible.²⁷ Bone biopsies of patients with known, advanced metastatic prostate cancer are performed with increasing frequency with yield exceeding 50 % (personal communications, [name] , University of Michigan) We estimate that in our population of patients biopsies will be accomplished in approximately 25% of cases of suspicious lesions because of their likely small size or difficult location and targeting . Based on our personal experience and personal communications we anticipate extremely high willingness of patients to undergo biopsy of suspected lesions.

The presence of histologically proven metastasis will be considered the “gold standard” for the confirmation of metastasis. However since majority of patients will not be able to undergo biopsies we will utilize two additional strategies to confirm the interpretation of imaging studies.

10.2.PSA Response To Salvage Radiation Therapy

The majority of our population of patients (unless biopsy proven metastases are discovered) will be offered salvage radiation therapy to the prostate bed. The concept of this therapy is that all the recurrent cancer cells may be located in the radiation field around prostate bed. Therefore the expected result of salvage RT is PSA level becoming undetectable (<0.04 ng/dL) within 6-8 weeks following completion of therapy.

Possible scenarios:

- a) The undetectable PSA level following salvage RT would be a very strong indicator that any visible abnormalities outside of the radiation field are false positives. If those lesions were “real” metastases (even extremely small) they would be expected to produce detectable amounts of PSA.
- b) If PSA does not become undetectable (< 0.04 ng/dL) in patients with completely normal scans that would be considered false negative.
- c) In patients who have abnormalities visible on the scans and inwhom salvage RT to prostate bed does not result in undetectable PSA level, then it is highly likely that the visible lesions are indeed true positives (likely sources of persistent PSA elevation). This scenario is the most difficult to interpret, because it is possible (but in my opinion much less likely) that the source of PSA is related to invisible metastases and identified lesions are benign.

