Patients who were classified as having negative bone scan and CT scan (estimated $\geq 90\%$ of patients) will undergo MRI (axial MRI and WB MRI) and F-18 NaF PET/CT. The outcome of these studies will be reported as 1) consistent with visible recurrence, 2) indeterminate 3) negative. In cases of findings consistent with visible recurrence or indeterminate a biopsy of the lesion of interest will be recommended if feasible. Any enrolled patient without a positive biopsy will be followed and their treatment (at discretion of treating physician), PSA values and outcome will be recorded to evaluate the scan result specificity and sensitivity in relation to additional information provided with follow-up (e.g. if patients undergo Salvage Radiation Therapy, PSA response will be recorded which will have significant implication in the interpretation of radiologic findings (see 10). Subsequently all patients without biopsy proven metastasis will undergo follow up imaging studies (the type of imaging to be recommended by radiologist)) within 4-6 months to reassess any abnormalities in the context of time, ongoing therapy or no therapy.

Sample Size:

Total Sample size is 56. Anticipated accrual is 2-3 patients a month.

Estimated Duration of the Study

24 months

Summary of Subject Eligibility Criteria:

Patients with 2 PSA values ≥ 0.2 ng/mL at least 4 weeks after surgery will be evaluated. Patients who were started on androgen deprivation therapy will not be allowed on this protocol. Patients who have started radiographic evaluation and underwent CT scan and/ or BS prior to registration to the study will be able to participate under a late registration provision, provided that WB/axial MRI and F-18 NaF PET/CT can be completed within 4 weeks of the CT scan and BS.

Investigational Product Dosage and Administration:

Not Applicable.

Clinical Observations and Tests to be Performed:

CT of the chest, abdomen and pelvis and bone scan. Targeted X Rays if suggested by the radiologist. If negative, WB/axial MRI and F-18 Sodium Fluoride PET /CT. Biopsy of suspected lesions will be performed if feasible, and repeat scans will be performed for patients with suspicious lesions.

Statistical Considerations:

Sponsor/Licensee:

City of Hope

Case Report Forms

Table of Contents

SECTION	PAGE
1.0 Objectives	8
2.0 Background.....	9
2.1 Introduction/Rationale for Development	9
2.2 Overview of Proposed Study	11
3.0 Patient Eligibility	12
3.1 Inclusion Criteria	12

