Currently at City of Hope, patients who present with a PSA level of ≥ 0.2 ng/mL after radical prostatectomy typically undergo computed tomography scan (CT) of the abdomen and pelvis, bone scan (BS), targeted X-rays (TXR), and occasionally Prostascint scanning, with the primary goal of excluding the presence of metastatic disease. However, these imaging modalities often fail to detect metastatic disease, especially early in the course of PC recurrence when the cancer burden is low.⁵ The value of abdominal and pelvic CT in the detection of metastases in patients with biochemically-recurrent PC is low, especially when PSA levels are < 10 ng/mL.⁶ The detection of metastatic bone cancer with BS is low because it detects bone deposits from osteoblasts, not directly from cancer cells.⁷ BS is positive in $< 1\%$ of patients who present with biochemically-recurrent PC and a PSA level of < 10 ng/mL.⁵ Prostascint scanning has significant limitations because it only recognizes the intracellular domain of prostate specific membrane antigen (PSMA) and, likely due to the low detection rate, Prostascint scans do not correlate with the efficacy of salvage RT in PC.⁸ As a result, the reported long-term success rate of salvage RT (in patients with negative CT scan and bone scan) ranges from 10-50%. This suggests that the majority of patients (50-90%) with biochemically-recurrent PC have occult metastases that are not visualized by standard imaging approaches,^{9,10,11} It is therefore clinically very important to improve the accuracy of radiologic assessment of patients with biochemically recurrent PC. This may have significant importance in the appropriate selection of patients for local salvage therapy or systemic treatments. Our

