5.3 Subject Follow-Up

Patients will be followed clinically and will undergo periodic laboratory and radiographic tests until week 52 or until disease progression requiring therapy (see Study calendar 9.0).

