10.2 Follow-up scans

Evolution of lesions over the period of time provides invaluable help in the verification of original interpretation of the scans even in the absence of biopsy. Therefore all the patients will undergo follow up scans (the type advised by radiologist) 4-6 months after registration to the protocol. These scans will be interpreted in the context of ongoing therapy (i.e. hormonal therapy) or observation. Several possible scenarios will allow us to interpret and verify the findings on the original scans.

- a) The persistence, growth, increase in numbers and intensity of enhancement of lesions in patients on observation would strongly favor the interpretation of a true positive finding.
- b) Complete stability over time or resolution of lesions without ongoing therapy would strongly favor false positive interpretation.
- c) Evolution of lesions (regression, radiologic signs of healing in the context of ongoing hormonal therapy (and lack of any history of trauma) would strongly support the interpretation of true positive scans
- d) Complete stability of lesions despite ongoing hormonal therapy would favor false positive interpretation

By combining these three elements of verification of original interpretation of WB/axial MRI and F-18 NaF PET/CT we will be able to provide the most robust assessment of sensitivity and specificity of these imaging modalities in the literature that may prove to be quite useful in the management of patients with biochemically recurrent prostate cancer.

Table 1

Interpretation of Imaging with WB/axial MRI and F-18 NaF PET/CT based on subsequent biopsy, therapy and follow up imaging (not all patients will be classified as below depending on additional systemic therapy given)

Original MRI/PET Interpretation	Biopsy	PSA response to salvage RT	Follow up scans	FINAL Interpretation of Baseline MRI/PET	
Mets	+	NA	Regardless	TP	
			Mets	Indeterminate	
			Indeterminate	FP	
			No mets	FP	
		≥ 0.04	Mets	TP	
	- or NA		Indeterminate	TP	
			No mets	Indeterminate	
	NA	Mets	TP		
		Indeterminate	TP		
		No mets	FP		
Indeterminate	+	NA	Regardless	TP	
			Mets	Indeterminate	
			Indeterminate	FP	
		≥ 0.04	No mets	FP	
			Mets	TP	
	- or NA	≥ 0.04	Indeterminate	TP	
			No mets	Indeterminate	
		NA	Mets	TP	
			Indeterminate	Indeterminate	
			No mets	FP	
Negative	N/A	<0.04	Mets	Indeterminate	
			Indeterminate	TN	
			No mets	TN	
		≥ 0.04	Mets	FN	
			Indeterminate	FN	
			No mets	Indeterminate	
		NA	Mets	Indeterminate	
			Indeterminate	TN	

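### The final-interpretation table has no state for a PSA that becomes undetectable after salvage RT and then rises, so such a man can be finalised as true negative or false positive

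*Combined protocol and SAP*

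**What the plan says.** Section 10.2 (PSA Response To Salvage Radiation Therapy) states: "Therefore the expected result of salvage RT is PSA level becoming undetectable (<0.04 ng/dL) within 6-8 weeks following completion of therapy". Two of its scenarios turn this into a verification rule. Scenario (a), for men with visible lesions: "The undetectable PSA level following salvage RT would be a very strong indicator that any visible abnormalities outside of the radiation field are false positives". Its reason is that true metastases, however small, should make measurable PSA. Scenario (b), for men with normal scans: "If PSA does not become undetectable (< 0.04 ng/dL) in patients with completely normal scans that would be considered false negative".

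The final-interpretation Table 1, under section 10.2 (Follow-up scans), combines four things: the baseline MRI/PET reading, biopsy, a column headed "PSA response to salvage RT", and the follow-up scan. The PSA column has three states (<0.04, ≥0.04, NA) and no date. The table's only exemption is for men given additional systemic therapy.

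The study calendar (section 9.0) draws PSA before the study and at weeks 16-24, 28-36 and 40-52. Section 5.3 provides "periodic laboratory and radiographic tests until week 52", or until progression that needs therapy. The synopsis says of men without a positive biopsy that "PSA values and outcome will be recorded to evaluate the scan result specificity and sensitivity". No section says how a PSA rise after an undetectable value changes a label.

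**The concern.** The table asks whether PSA became undetectable. It does not ask whether PSA stayed so. A man who reaches <0.04 after RT and is detectable again at week 40-52 no longer meets the premise of scenario (a), because something is producing PSA. Scenario (b) is not triggered either, because his PSA did become undetectable. The background also reasons from durable outcome. Section 2.1 says that "the reported long-term success rate of salvage RT (in patients with negative CT scan and bone scan) ranges from 10-50" percent, and infers occult metastases in the remaining 50-90%.

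The verified true-negative (TN) and false-positive (FP) counts are at stake, and through them the sensitivity and specificity assessment that section 10.2 promises. The evaluation of treatment results that section 12.0 adds to the determination of success also draws on them. PSA carries much of this verification: section 10.1.1 expects biopsy in about 25% of cases with suspicious lesions, and section 10.2 says most men will be offered salvage RT. With no PSA date fixed, the choice of which value to enter could also be made after the results are known.

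**Working it through.** **1. The plan's own design figures.** Section 12.0 requires at least 4 positives among 45 men. The exact binomial gives P(X ≥ 4 | n = 45, p = 0.03) = 0.0456 and P(X ≥ 4 | n = 45, p = 0.15) = 0.9215. The stated bounds (type I error below 5%, power above 86%) hold. The issue lies in the classification rule.

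**2. The same man under two PSA readings.** These are the Table 1 rows with no positive biopsy and a follow-up scan not read as metastatic. In the extracted text the <0.04 label is missing from the first two blocks; I infer it from row order and from the Negative block.

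| Baseline MRI/PET | Follow-up scan | PSA <0.04 | PSA ≥0.04 |
|---|---|---|---|
| Mets | Indeterminate | FP | TP |
| Mets | No mets | FP | Indeterminate |
| Indeterminate | Indeterminate | FP | TP |
| Indeterminate | No mets | FP | Indeterminate |
| Negative | Indeterminate | TN | FN |
| Negative | No mets | TN | Indeterminate |

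All six labels depend on which PSA is entered. The other rows are not exposed: a positive biopsy gives TP, and PSA <0.04 with metastases at follow-up gives Indeterminate.

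**3. Whether the follow-up scan would catch the relapse.** It is due at weeks 16-24 from registration. Assume that RT starts at weeks 8-16 and lasts 6-8 weeks (neither is in the documents). A reading 6-8 weeks after RT then falls between week 8 + 6 + 6 = 20 and week 16 + 8 + 8 = 32. The scan would often come before or around that reading, so it cannot be relied on to show a later relapse. The week 40-52 PSA always follows the reading, and the week 28-36 PSA usually does.

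**4. How many early responders might fail later.** Let u be the share undetectable early (not in the documents; assumed 50-80%) and s the long-term success rate (10-50%, section 2.1). The share of early responders who later fail is 1 − s/u:
- u = 0.5, s = 0.5: 0%
- u = 0.6, s = 0.3: 50%
- u = 0.8, s = 0.1: 87.5%

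These are long-term figures. Only some of the failures would appear by week 52.

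**5. Effect on specificity, TN/(TN + FP).** Assume 30 irradiated scan-negative men with u = 0.6, so 18 TN, and 3 FP. As written, 18/21 = 85.7%. Now take relapsers out of the verified cells:
- 20% out of both cells: 14.4/(14.4 + 2.4) = 85.7%
- 50% out of both cells: 9/(9 + 1.5) = 85.7%
- 20% out of TN only: 14.4/17.4 = 82.8%
- 50% out of TN only: 9/12 = 75.0%
- 20% out of TN and 1 of 3 FP: 14.4/16.4 = 87.8%

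Specificity can stay, fall or rise. What does follow is that the number of men verified as TN or FP shrinks, here from 21 to 16.8 or 10.5 in the two equal-relapse cases.

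**The case against.** Several objections are sound and limit the point.

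- **The 6-8 weeks is not a dated rule.** Section 10.2 calls it an expected result, Table 1 has no time point, and no PSA is scheduled relative to the end of RT. A reader might infer that the plan fixes the label at 6-8 weeks and forbids revision. The documents do not say so. They are silent on a later rise, and scenario (b) and Table 1 leave it nowhere to go.
- **Specificity is not shown to be inflated.** A reader might infer inflation because relapsing scan-negative men sit in TN. Relapsing scan-positive men sit in FP, however, and step 5 shows that the net direction is open.
- **The primary count is not directly changed.** Section 12.0 counts men positive on the newer scans, and TN labels do not enter. One can construct a power loss: if only verified positives counted and 20% of true positives were labelled FP in this way, power at a 15% rate would fall from 92.2% to 80.5%. The plan states no such counting rule. The remedy below moves FP to Indeterminate, so in itself it would not restore those positives.
- **A PSA rise does not locate disease.** It may be local failure, in which case TN or FP for metastasis was right. This argues against relabelling to FN or TP, but not against withholding a verified label.
- **Sensitivity and specificity are not listed objectives** in section 1.0, and the secondary endpoints are exploratory. Section 10.2 nevertheless promises a robust assessment of both.
- **The systemic-therapy exemption** may cover some treated relapsers. It does not cover a man under observation with a rising PSA.

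**Conclusion.** The point holds as a gap in a stated classification rule. A man whose PSA becomes undetectable after salvage RT and returns to ≥0.04 by week 52 can be finalised as FP (baseline Mets or Indeterminate) or TN (baseline Negative). This conflicts with the premise of scenario (a), and the PSAs that would reveal it are already scheduled.

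The direct effect is on the verified TN and FP counts. Specificity is computed from them, but its change cannot be sized or signed from the documents. Sensitivity moves only if metastasis is established in such men or if the later PSA is the value entered. The number of men affected depends on the early undetectable rate and on relapse by week 52. Neither is given, and the range in step 4 includes zero. The conclusion itself rests only on the text of section 10.2, the table rows (with the inferred <0.04 labels) and the calendar. The change is worth making because it is cheap and can be set before results are known.

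**What to change.** In section 10.2 and as a footnote to the final-interpretation table:

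1. Define <0.04 as undetectable after RT and not back to ≥0.04 at any later scheduled PSA through week 52.
2. Do not finalise a man with a later rise as FP or TN. Label him Indeterminate unless biopsy or follow-up imaging establishes metastasis.
3. Let a rise first seen at the last scheduled PSA (weeks 40-52) also block FP and TN, even if unconfirmed, because no later scheduled value exists. A clinically drawn PSA may confirm it where available.
4. Report the classification based on the early PSA alone as a sensitivity analysis.

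The plan should also say how a missing later PSA is handled. Separately, the cut-off is in ng/dL while eligibility is in ng/mL (0.04 ng/dL = 0.0004 ng/mL); these need to be reconciled.

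Cost: wording only, with no new visits or samples and no change to care. Final labels wait until week 52. A few more men end as Indeterminate, including some whose rise is only local failure or assay noise.

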Current imaging modalities have low sensitivity to detect recurrence in patients who have rising PSA after prostatectomy as evidenced by a high percentage of patients who fail to respond to salvage local therapy. While not routinely used, MRI is part of the NCCN guidelines for evaluating disease in this patient population, and F-18 NaF PET/CT is FDA approved for the detection of bone metastasis, the most common site of distant recurrence. As a result, we will implement the routine use of these new imaging modalities in addition to the historically used imaging tests in a prospective cohort to document the added benefit. We hypothesize that combination of WB/axial MRI and F-18 NaF PET/CT will localize the site of recurrence in significant proportion of these patients.
Objectives:

Primary Objective : To determine the proportion of patients with biochemically-recurrent PC in whom imaging with WB/axial MRI and F-18 NaF PET/CT results in detection of metastatic disease not visualized on CT scan and bone scan.
 
Secondary Objectives:
 
To estimate the percent of eligible patients with negative, indeterminate and positive CT scan/bone scan and targeted X-rays if done.
 
To determine the proportion of patients with biochemically recurrent PC in whom recurrence in the prostate bed can be visualized using WB/axial MRI in the absence of detection using CT scan.
 
To correlate the presence of metastatic disease detected using WB/axial MRI and/or F-18 NaF PET/CT with the predicted 6-year probability of progression-free survival based on the Memorial Sloan Kettering Cancer Center salvage RT PC nomogram, and with PSA levels at baseline.
 
To compare the role of axial MRI of the spine to WB/axial MRI with respect to their ability to identify sites of disease. Similarly, to evaluate the relative contribution of F-18 NaF PET and MRI.

Patients with two PSA values ≥ 0.2 ng/mL at least 4 weeks after prostatectomy will undergo imaging studies including CT of the chest, abdomen and pelvis and bone scan. Targeted X Rays will be obtained in case of equivocal findings if suggested by the radiologist. The results of the scans will be classified as: 1) consistent with visible recurrence, 2) indeterminate 3) negative.

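### The cut-off for undetectable PSA after salvage radiotherapy is printed in ng/dL, 100-fold below the same number on the ng/mL scale used for every other PSA value

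*Combined protocol and SAP*

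**What the plan says.** Three places in Section 10 matter. All concern verification of the MRI and NaF PET/CT readings when there is no positive biopsy.

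- Section 10.2 (PSA Response To Salvage Radiation Therapy) states that the "expected result of salvage RT is PSA level becoming undetectable (<0.04 ng/dL) within 6-8 weeks following completion of therapy".
- Scenario (b) of that section uses the same number and unit to define a false negative: "If PSA does not become undetectable (< 0.04 ng/dL) in patients with completely normal scans". Scenario (a) gives no number: "The undetectable PSA level following salvage RT would be a very strong indicator" that abnormalities outside the radiation field are false positives. Scenario (c) gives no number either.
- Table 1 under 10.2 Follow-up scans assigns the final label (TP, FP, TN, FN or Indeterminate). Its column "PSA response to salvage RT" splits patients at 0.04. Neither the header nor any legible cell shows a unit.

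Elsewhere PSA is in ng/mL. The synopsis, for example, has "Patients with two PSA values ≥ 0.2 ng/mL at least 4 weeks after prostatectomy will undergo imaging studies".

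On how widely the rule applies, the PSA section says: "The majority of our population of patients (unless biopsy proven metastases are discovered) will be offered salvage radiation therapy to the prostate bed". Section 10.2 Follow-up scans claims that, with biopsy, PSA response and follow-up imaging combined, "we will be able to provide the most robust assessment of sensitivity and specificity of these imaging modalities in the literature". The table caption limits this: "not all patients will be classified as below depending on additional systemic therapy given".

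**The concern.** The cut-off carries a unit not used for PSA anywhere else in the protocol, and nothing explains the change. The table that applies it has no unit. One reader could carry ng/dL from the text into the table, while another could assume ng/mL from the rest of the protocol. Both would be following the document, and they would classify some patients differently.

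The threshold feeds the scan-accuracy labels. Section 10.1.1 expects biopsy in only about 25% of cases with suspicious lesions, and PSA response is one of two further strategies named to confirm the readings. Section 12 adds that treatment results, when applicable, enter the final determination of success. The labels, and any sensitivity or specificity built on them, therefore depend on which unit is used.

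**Working it through.** The plan derives no figure from this cut-off, so there is no stated result to reproduce. The check is a unit conversion, a count of printed values and a reading of the table.

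**1. Conversion.** 1 dL = 100 mL, so 0.04 ng/dL = 0.04 / 100 = 0.0004 ng/mL.

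**2. Against the entry threshold of 0.2 ng/mL (Section 3.1.2).**
- As printed: 0.2 / 0.0004 = 500, so the cut is 1/500 of entry.
- If 0.04 were in ng/mL: 0.2 / 0.04 = 5, so the cut is 1/5 of entry.
- Ratio of the two readings: 0.04 / 0.0004 = 100.

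**3. Units printed with PSA values.**

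| Place | Values | Unit |
|---|---|---|
| Synopsis, study design | 0.2 | ng/mL |
| Synopsis, eligibility summary | 0.2 | ng/mL |
| Section 2.1 | 0.2, 0.2, 10, 10 | ng/mL |
| Section 3.1.2 | 0.2 | ng/mL |
| Section 10.2 (PSA response) | 0.04, 0.04 | ng/dL |

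That is 1 + 1 + 4 + 1 = 7 values in ng/mL and 2 in ng/dL.

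**4. Range in dispute.** A PSA of at least 0.0004 and below 0.04 ng/mL is at or above the cut as printed, but below it if the cut is in ng/mL. For example, 0.01 ng/mL = 1 ng/dL, which is 1 / 0.04 = 25 times the printed cut. With normal scans, scenario (b) makes this patient a false negative as printed, but not on the ng/mL reading.

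**5. Effect in the table.** Only the Negative block has both PSA rows fully legible. For a PSA in the disputed range:

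| Follow-up scan | Cut in ng/mL (PSA below cut) | Cut in ng/dL (PSA at or above cut) |
|---|---|---|
| Mets | Indeterminate | FN |
| Indeterminate | TN | FN |
| No mets | TN | Indeterminate |

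All 3 of 3 labels change. The Mets and Indeterminate blocks appear to behave in parallel, but their below-cut cells cannot be read in the extracted text and are not counted.

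**6. Primary analysis.** The rule in Section 12 (at least 4 of 45, with 3% as the discouraging rate and 15% as the rate for power) contains no PSA term. Its type I error and power are unaffected.

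**The case against.** The strongest reply is that this is a slip with little practical effect. The table prints a bare 0.04. Staff who compare it with PSA values recorded on the protocol's usual ng/mL scale would all reach the same labels, and the harm would be limited to contradictory text. That is possible, but nothing in the documents ensures it: the only unit ever attached to 0.04 is ng/dL.

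A second reply is that the disputed range may be empty. The text equates the cut with undetectable. If the assay's reporting limit were 0.04 ng/mL, no patient would have a measured value between 0.0004 and 0.04 ng/mL. The documents name no assay limit, so this is an assumption. With a lower limit, some patients could fall in the range. The example of 0.01 ng/mL presupposes a lower limit.

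Third, the reach is modest. Sensitivity and specificity are not among the objectives in Section 1.0, the caption says not every patient will be classified by the table, and Section 12 gives no rule linking the PSA cut-off to the primary count. All of this stands and limits the weight of the point.

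Fourth, scenario (b) and the table already differ whatever the unit. The text calls normal scans with a detectable PSA a false negative outright, while the table gives Indeterminate when follow-up shows no metastases. That is a separate inconsistency and does not explain the unit.

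None of these replies removes the conflict between the two printed units.

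**Conclusion.** The point holds. The cut-off is printed twice in a unit 100-fold out of line with the other seven PSA values, and the table that applies it shows no unit. This is a decision threshold in the rule for labelling scan results, so it matters more than a slip in the background text. The size is a factor of 100 in the threshold and 3 of 3 changed labels in the Negative block for a PSA from 0.0004 to just under 0.04 ng/mL.

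The label changes are conditional: they arise only if the ng/dL reading is applied to the table and the assay reports values in that range. The number of patients affected cannot be estimated from the documents. The documents alone do not prove which unit was intended, although the consistent use of ng/mL elsewhere makes a misprint the likely explanation. This should be corrected, but it does not threaten the primary analysis.

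**What to change.** The sponsor should confirm the unit of the 0.04 cut-off, then:

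1. reconcile the unit at both places in Section 10.2 (PSA Response To Salvage Radiation Therapy) with the ng/mL scale used for PSA in the synopsis and Sections 2.1 and 3.1.2;
2. print that unit in the PSA-response column of Table 1 under 10.2 Follow-up scans.

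The cost is two unit corrections and one column label. No new data, visits or patients are required, and Section 12 does not change.

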2.0 Background

2.1 Introduction/Rationale for Development

Background

Each year, approximately 32,000 men in the United States will have a recurrence of prostate cancer (PC) after radical prostatectomy.¹ For most of these patients the only manifestation of recurrent disease is an increasing level of serum prostate specific antigen (PSA) in the blood detected through routine monitoring after surgery. A PSA level of ≥ 0.2 ng/mL is considered the threshold for biochemical recurrence.² For those patients who have a recurrence, some will have disease that is initially confined to the prostate bed and pelvis. Patients who have not previously received adjuvant radiation therapy (RT) can potentially be cured by local salvage RT. However, this treatment approach is complicated by the inability to distinguish between those patients with an isolated local recurrence and those patients with occult distant metastases who will not benefit from salvage RT.^{3,4} Therefore accurate localization of recurrent disease has significant therapeutic implications.

Currently, there is no consensus regarding the use of specific imaging techniques in patients with biochemically recurrent prostate cancer. National Comprehensive Cancer Center (NCCCN) guidelines suggest obtaining “+/- CT scan, +/- bone scan, +/- Ultrasound, +/- MRI” indicating lack of any meaningful guidelines. In addition, in 2011, the FDA approved F-18 NaF PET/CT for the detection of bone metastases for Medicare beneficiaries through the Coverage with Evidence Development/National oncologic PET Registry program (NOPR) adding to the available options with limited guidelines.

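### Table 1 drops the outside-the-field condition of scenario (a), so a real lesion inside the salvage-RT field that RT cleared can be scored false positive

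*Combined protocol and SAP*

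**What the plan says.** The section headed PSA Response To Salvage Radiation Therapy (one of two numbered 10.2) says that most men without biopsy-proven metastases "will be offered salvage radiation therapy to the prostate bed". The result hoped for is "PSA level becoming undetectable (<0.04 ng/dL) within 6-8 weeks following completion of therapy". Scenario (a) then says that such a PSA strongly indicates that "any visible abnormalities outside of the radiation field are false positives". The reason given is that if these lesions were real metastases, "they would be expected to produce detectable amounts of PSA".

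Table 1 at the end of section 10.2 Follow-up scans is titled "Interpretation of Imaging with WB/axial MRI and F-18 NaF PET/CT based on subsequent biopsy, therapy and follow up imaging". It assigns TP, FP, TN, FN or Indeterminate from four inputs: original reading, biopsy, PSA response to salvage RT, and follow-up scans. Its one caveat is that "not all patients will be classified as below depending on additional systemic therapy given".

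Sections 2.2 and 10 define the positive MRI/PET reading as consistent with recurrence. Table 1 labels it Mets.

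**The concern.** The argument in scenario (a) works only for tissue that RT did not treat. An untreated metastasis would go on making PSA, so an undetectable PSA speaks against it. For a lesion that was irradiated, an undetectable PSA and a cleared scan are what successful treatment of real cancer would produce. The text keeps the two cases apart and the table does not.

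Table 1 is the only tabulated rule for verifying the baseline readings. Section 10.2 Follow-up scans promises sensitivity and specificity from the combined verification, and the Synopsis gives the same purpose for the follow-up data. Section 12 adds that follow-up scans and treatment results enter the final determination of success.

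**Working it through.** No figure in the plan measures this point, so the check sets the passages side by side.

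**1. The PSA <0.04 cells.** In the text available here, the <0.04 label is missing from the Mets and Indeterminate blocks of Table 1. I infer it from the Negative block, where it is printed, from the ≥0.04 rows that follow, and from scenario (a). I treat its absence as an artefact of reading the PDF. For a biopsy that is negative or not available, the cells are:

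| Original reading | PSA after RT | Follow-up Mets | Follow-up Indeterminate | Follow-up No mets |
|---|---|---|---|---|
| Mets | <0.04 | Indeterminate | FP | FP |
| Indeterminate | <0.04 | Indeterminate | FP | FP |
| Mets | ≥0.04 | TP | TP | Indeterminate |
| Indeterminate | ≥0.04 | TP | TP | Indeterminate |

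**2. A real in-field lesion cleared by RT.** The original reading is Mets or Indeterminate, there is no positive biopsy, PSA falls below 0.04, and the follow-up scan shows No mets or is equivocal. All four of these paths end in FP. Scenario (a) supports FP only if the lesion was outside the field.

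**3. Can another rule rescue it?** A positive biopsy gives TP, but section 10.1.1 expects biopsy in only about 25% of suspicious lesions. If a fraction y of those biopsies is positive, the share of such lesions scored FP is 1 − 0.25y:
- y = 1: 1 − 0.25 = 75%
- y = 0.5: 1 − 0.125 = 87.5%
- y = 0: 100%

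The values of y are assumptions. The follow-up rules do not help either. Rule (b) links resolution to a false positive only when no therapy is ongoing, and rule (c) counts regression under hormonal therapy as support for a true positive. Neither says how to read a lesion that cleared after RT.

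**4. Are in-field findings foreseeable?** Yes. Section 2.1 says that "some will have disease that is initially confined to the prostate bed and pelvis". Secondary objective 2 concerns prostate-bed recurrence seen on MRI but not on CT. The Synopsis says of men without a positive biopsy that "their treatment (at discretion of treating physician), PSA values and outcome will be recorded", so the protocol does not fix the treatment.

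**5. Direction in the PSA <0.04 cells.** Let a, b and c be the TP, FP and TN counts, and suppose k real metastases inside the field move from TP to FP. Positive predictive value goes from a/(a+b) to (a−k)/(a+b), and specificity from c/(c+b) to c/(c+b+k). Both fall.

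**6. Direction in the PSA ≥0.04 cells.** A benign in-field finding in a man whose PSA persists because of occult disease elsewhere is scored TP if the follow-up scan is read as Mets or Indeterminate. Scenario (c) itself admits that visible lesions may be benign while invisible disease makes the PSA. This error favours the new scans.

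**7. The section 12 rule.** At least 4 positives among 45 men gives an exact type I error of 0.0456 at a 3% rate and power of 0.9215 at 15%. These agree with the stated limits of under 5% and over 86%. The rule counts men with metastatic disease on the newer scans and does not refer to Table 1.

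**The case against.** The strongest reply is that the label Mets already carries the missing condition. The primary objective is metastatic disease, the only RT target named is the prostate bed, and bed recurrence has its own objective. If a bed lesion is called a metastasis and then clears with RT, FP for metastasis is a defensible score. This stands as far as it goes. It still leaves indeterminate findings in or near the bed, and any metastasis within the field. It also depends on a mapping that the documents never state, because the reading is defined as recurrence and tabulated as Mets.

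It is also fair that nothing in the documents says the field reaches pelvic lesions, that the affected cells are narrow, and that sensitivity and specificity are not among the listed objectives or section 12 endpoints. These points limit the severity. They do not reconcile the table with scenario (a).

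A reader might put a number on the harm. About seven positives are expected (0.15 × 45 = 6.75; 0.15 × 49 = 7.35), and one to three of them might be supposed to lie in the field. The documents support no such share. The 15% rate refers to detected metastases, whereas the likeliest route to this error is an indeterminate finding near the bed.

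**Conclusion.** Table 1 contradicts the rationale of scenario (a) as written. A real in-field lesion cleared by RT can be scored FP by three routes: an indeterminate finding in or near the bed, a bed recurrence entered under Mets, or a metastasis within the field. In the PSA <0.04 cells this biases specificity and positive predictive value down. How far cannot be computed without the in-field share.

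Two stronger readings are not supported. One is that the missing input always works against MRI/PET. It does so in the PSA <0.04 cells, but in the ≥0.04 cells the error can favour the new scans. The other is that the trial's type I error or power is wrong for this reason. The numerical rule does not use Table 1, so only the accuracy assessment and the unquantified final determination in section 12 are exposed.

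The conclusion rests on the inferred <0.04 label and on there being no stated exclusion of in-field lesions; I found none. Severity: moderate.

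**What to change.** Before any baseline reading receives its final classification:

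- Record for each abnormal lesion, from the RT record, whether it lay inside the salvage-RT field.
- State how a recurrence reading maps to Mets or to local recurrence in Table 1.
- Apply the PSA <0.04 FP cells only to out-of-field lesions.
- Score an in-field suspected metastasis or indeterminate lesion with PSA <0.04 and no positive biopsy as Indeterminate.
- Report prostate-bed findings under secondary objective 2, not as FP for metastasis.
- In a man with lesions both inside and outside the field, classify each lesion first and then form the patient-level result by a stated rule. A single yes/no question on whether all lesions were out of field would switch off the FP cells for the out-of-field lesion too.
- Note in the same place that PSA ≥0.04 is weaker evidence for an in-field lesion, and say how those cells are to be read.

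The cost is one CRF field, a split of a few cells, and a few more Indeterminate classifications. Patient care does not change.
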